10.2 MANAGEMENT OF IMMUNE-RELATED ADVERSE EVENTS

Management of immune-related adverse event toxicities associated with anti-PD-1 mAbs are presented below. **BI 754091 and BI 754111 should be permanently discontinued for Grade 3-4 pneumonitis, Grade 3-4 adrenal insufficiency, Grade 4 diabetes mellitus, any grade encephalitis, Grade 4 hypophysitis, Grade 4 rash, Grade 3-4 or recurrent colitis of any grade, any recurrent Grade 3-4 AE, transaminase increased >5 times ULN or total bilirubin >3 times ULN (unless unequivocally attributably to another cause), inability to taper steroids to 10 mg or less prednisone or equivalent within 12 weeks, or persistent Grade 2-3 AEs that do not recover to Grade 1 or less within 12 weeks.**

- Pneumonitis:
 - For Grade 2 events, treat with systemic corticosteroids. When symptoms improve to Grade 1 or less, steroid taper should be started and continued over no less than 28 days.
 - Add prophylactic antibiotics for opportunistic infections in the case of prolonged steroid administration.
 - For Grade 3-4 events immediately treat with i.v. steroids. Administer additional anti-inflammatory measures, as needed.
 - BI 754091 and BI 754111 should be permanently discontinued for Grade 3-4 pneumonitis, inability to taper steroids to 10 mg or less prednisone or equivalent within 12 weeks, or persistent Grade 2 AEs that do not recover to Grade 1 or less within 12 weeks.
- Diarrhea/Colitis:

Subjects should be carefully monitored for signs and symptoms of enterocolitis (such as diarrhea, abdominal pain, blood or mucus in stool, with or without fever) and of bowel perforation (such as peritoneal signs and ileus).

 - All subjects who experience diarrhea/colitis should be advised to drink liberal quantities of clear fluids. If sufficient oral fluid intake is not feasible, fluid and electrolytes should be substituted via i.v. infusion. For Grade 2 or higher diarrhea, consider gastro-intestinal (GI) consultation and endoscopy to confirm or rule out colitis.
 - For Grade 2 diarrhea/colitis that persists greater than 3 days, administer oral corticosteroids.
 - For Grade 3 or 4 diarrhea that persists >1 week, treat with i.v. steroids followed by high-dose oral steroids.
 - For Grade 3 or 4 colitis, or recurrent colitis of any grade, permanently discontinue BI 754091 and BI 754111, and immediately treat with i.v. steroids followed by high-dose oral steroids.
 - When symptoms improve to Grade 1 or less, steroid taper should be started and continued over no less than 28 days.
 - BI 754091 and BI 754111 should be permanently discontinued for Grade 3-4 or recurrent colitis of any grade, inability to taper steroids to 10 mg or less prednisone or equivalent within 12 weeks, or persistent Grade 2-3 AEs that do not recover to Grade 1 or less within 12 weeks.
- Type 1 diabetes mellitus (if new onset, including diabetic ketoacidosis) Grade 3, or \geq Grade 3 hyperglycaemia, if associated with ketosis (ketonuria) or metabolic acidosis

Proprietary confidential information © 2020 Boehringer Ingelheim International GmbH or one or more of its affiliated companies

- For Type 1 diabetes mellitus Grade 3-4 or Grade 3-4 hyperglycaemia
 - Insulin replacement therapy is recommended for Type I diabetes mellitus and for Grade 3-4 hyperglycaemia associated with metabolic acidosis or ketonuria.
 - Evaluate subjects with serum glucose and a metabolic panel, urine ketones, glycosylated haemoglobin, and C-peptide.
- BI 754091 and BI 754111 should be permanently discontinued for Grade 4 diabetes mellitus, any recurrent Grade 3 AE or persistent Grade 2-3 AE that does not recover to Grade 1 or less within 12 weeks.
- Hypophysitis:
 - For Grade 2 events, treat with corticosteroids. When symptoms improve to Grade 1 or less, steroid taper should be started and continued over no less than 28 days. Replacement of appropriate hormones may be required as the steroid dose is tapered.
 - For Grade 3 events, treat with an initial dose of *i.v.* corticosteroids followed by oral corticosteroids. When symptoms improve to Grade 1 or less, steroid taper should be started and continued over no less than 28 days. Replacement of appropriate hormones may be required as the steroid dose is tapered.
 - For Grade 4 events, permanently discontinue BI 754091 and BI 754111, and treat with an initial dose of *i.v.* corticosteroids followed by oral corticosteroids. When symptoms improve to Grade 1 or less, steroid taper should be started and continued over no less than 28 days. Replacement of appropriate hormones may be required as the steroid dose is tapered.
 - BI 754091 and BI 754111 should be permanently discontinued for Grade 4 hypophysitis, any recurrent Grade 3 AE, inability to taper steroids to 10 mg or less prednisone or equivalent within 12 weeks, or persistent Grade 2-3 AEs that do not recover to Grade 1 or less within 12 weeks.
- Hyperthyroidism or Hypothyroidism:
 - Thyroid disorders can occur at any time during treatment. Monitor subjects for changes in thyroid function (at the start of treatment, periodically during treatment, and as indicated based on clinical evaluation) and for clinical signs and symptoms of thyroid disorders.
 - For Grade 2 hyperthyroidism events (and Grade 3-4 hypothyroidism):
 - In hyperthyroidism, nonselective beta-blockers (e.g., propranolol) are suggested as initial therapy.
 - In hypothyroidism, thyroid hormone replacement therapy, with levothyroxine or liothyronine, is indicated per standard of care.
 - For Grade 3-4 hyperthyroidism
 - Treat with an initial dose of *i.v.* corticosteroid followed by oral corticosteroids. When symptoms improve to Grade 1 or less, steroid taper should be started and continued over no less than 28 days. Replacement of appropriate hormones may be required as the steroid dose is tapered.
 - BI 754091 and BI 754111 should be permanently discontinued for any recurrent Grade 3-4 AE, inability to taper steroids to 10 mg or less prednisone or equivalent within 12 weeks, or persistent Grade 2-3 AEs that do not recover to Grade 1 or less within 12 weeks.

Proprietary confidential information © 2020 Boehringer Ingelheim International GmbH or one or more of its affiliated companies

- Hepatic:
 - For Grade 2 events, monitor liver function tests more frequently until returned to baseline values (consider weekly).
 - Treat with *i.v.* or oral corticosteroids
 - For Grade 3-4 events, treat with *i.v.* corticosteroids for 24 to 48 hours.
 - When symptoms improve to Grade 1 or less, a steroid taper should be started and continued over no less than 28 days.
 - BI 754091 and BI 754111 should be permanently discontinued for any recurrent Grade 3-4 AE, transaminase increases >5 times ULN or total bilirubin >3 times ULN (unless unequivocally attributable to another cause), inability to taper steroids to 10 mg or less prednisone or equivalent within 12 weeks, or persistent Grade 2-3 AEs that do not recover to Grade 1 or less within 12 weeks.
- Renal failure or nephritis:
 - For Grade 2 events, treat with corticosteroids.
 - For Grade 3-4 events, treat with systemic corticosteroids.
 - When symptoms improve to Grade 1 or less, steroid taper should be started and continued over no less than 28 days.
 - BI 754091 and BI 754111 should be permanently discontinued for any recurrent Grade 3-4 AE, inability to taper steroids to 10 mg or less prednisone or equivalent within 12 weeks, or persistent Grade 2-3 AEs that do not recover to Grade 1 or less within 12 weeks.
- Adrenal insufficiency:
 - BI 754091 and BI 754111 should be permanently discontinued for Grade 3-4 adrenal insufficiency or persistent Grade 2 AEs that do not recover to Grade 1 or less within 12 weeks.
- Rash:
 - BI 754091 and BI 754111 should be permanently discontinued for Grade 4 rash, any recurrent Grade 3 AE or persistent Grade 2-3 AEs that do not recover to Grade 1 or less within 12 weeks.
- Encephalitis:
 - BI 754091 and BI 754111 should be permanently discontinued for any grade encephalitis.
- Infusion reactions:

Signs and symptoms usually develop during or shortly after drug infusion and generally resolve completely within 24 hours of completion of infusion.

In the event of an infusion-related reaction \leq Grade 2, treat the symptoms accordingly with antihistamine or corticosteroids if needed, the infusion rate of study drug(s) may be decreased by 50% or interrupted until resolution of the event and re-initiated at 50% of the initial rate until completion of the infusion. In patients experiencing infusion-related reactions \leq Grade 2, subsequent infusions may be administered at 50% of the initial rate. If an infusion related reaction is Grade 3 or higher in severity at any point during the study, permanently discontinue study drug(s).

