- Any factors that increase the risk of QTc prolongation or risk of arrhythmic events such as heart failure, hypokalaemia, congenital long QT syndrome, family history of long QT syndrome or unexplained sudden death under 40 years-of-age, or any concomitant medication known to prolong the QT interval
 - Ejection fraction <55% or the lower limit of normal of the institutional standard.
12. History of pneumonitis within the last 5 years
 13. History of severe hypersensitivity reactions to other mAbs
 14. Immunosuppressive corticosteroid doses (>10 mg prednisone daily or equivalent) within 4 weeks prior to the first dose of study treatment.
 15. Active autoimmune disease or a documented history of autoimmune disease, except vitiligo or resolved childhood asthma/atopy
 16. Active infection requiring systemic treatment (antibacterial, antiviral, or antifungal therapy) at start of treatment in this trial
 17. Known history of human immunodeficiency virus infection or an active hepatitis B or C virus infection
 18. Interstitial lung disease
 19. Chronic alcohol or drug abuse or any condition that, in the investigator's opinion, makes him/her an unreliable trial patient or unlikely to complete the trial or unable to comply with the protocol procedures
 20. Women who are pregnant, nursing, or who plan to become pregnant in the trial

Table 3.3.3: 1

Laboratory values demonstrating inadequate organ function

Laboratory Parameter	Values
Absolute neutrophil count	<1.5 x 10 ⁹ /L (<1500/mm ³)
Alanine aminotransferase (ALT)	>2.5 X ULN if no demonstrable liver metastases or >5 X ULN in the presence of liver metastases
Aspartate aminotransferase (AST)	>2.5 X ULN if no demonstrable liver metastases or >5 X ULN in the presence of liver metastases
Haemoglobin	<9 g/dL
International Normalized Ratio (INR) (only tested if clinically indicated)	>1.5 X ULN (If treated with anticoagulants, prolonged INR is acceptable)
Platelet count	<100 x 10 ⁹ /L
Serum Creatinine	>1.5 X ULN or estimated glomerular filtration rate (eGFR) <30 mL/min/1.73 m ² (Chronic Kidney Disease Epidemiology (CKD-EPI) Collaboration equation); confirmation of eGFR is only required when creatinine is >1.5 X ULN.
Total bilirubin	>1.5 X ULN, except for patients with Gilbert's syndrome who are excluded if total bilirubin >3.0 X ULN or direct bilirubin >1.5 X ULN

ULN = Upper Limit of Normal

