4.1.2.4 Dose modification for BI 754111 and BI 754091 treatments

There will be no dose reductions or escalations of BI 754091 or BI 754111 in any one patient. All patients (including patients allocated to a different dose of BI 754111 treatment during the on-treatment assessment phase (Cycle2) in Part 2), will take the recommended expansion phase dose of BI 754111 (determined in the 1381-0002 trial) starting from Cycle 3 onward.

The dose may be delayed for up to 6 weeks because of AEs, following discussion with the sponsor.

If treatment is held or discontinued due to an AE(s), both BI 754091 and BI 754111 will be held or discontinued together. If treatment is to be restarted after resolution (< Grade 1 or baseline) of the AE, both BI 754091 and BI 754111 must be started together.

The study treatments BI 754091 and BI 754111 should be permanently discontinued for CTCAE Version 5.0 Grade 3 or 4 pneumonitis, Grade 3 or 4 adrenal insufficiency, Grade 3 or 4 or recurrent colitis of any grade, Grade 4 diabetes mellitus, Grade 4 hypophysitis, Grade 4 rash, any grade encephalitis, any recurrent Grade 3 or 4 AE, transaminase values >5 times the ULN or total bilirubin >3 times ULN, inability to taper steroids to 10 mg or less prednisone or equivalent within 12 weeks, or persistent Grade 2 or 3 AEs that do not recover to Grade 1 or less within 12 weeks. Additional information of management of irAEs is provided in [Appendix 10.2](#).

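### For liver values above the stopping threshold that are unequivocally due to another cause, Protocol Section 4.1.2.4 requires permanent discontinuation and Appendix 10.2 exempts them

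*Protocol*

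**What the plan says.** The liver discontinuation criterion appears three times in the current protocol.

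- **Section 4.1.2.4 (dose modification).** The list of stopping reasons begins "The study treatments BI 754091 and BI 754111 should be permanently discontinued for CTCAE Version 5.0 Grade 3 or 4 pneumonitis" and includes "transaminase values >5 times the ULN or total bilirubin >3 times ULN". No condition on cause is attached to the liver criterion. The paragraph ends with a pointer to the appendix: "Additional information of management of irAEs is provided in" Appendix 10.2.
- **Appendix 10.2, opening paragraph.** Nearly the same list for the same two drugs, but the liver criterion carries the qualifier "unless unequivocally attributably to another cause" (the spelling is the protocol's).
- **Appendix 10.2, Hepatic item.** The criterion and its exception are stated again.

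Three other places bear on the point. Section 3.3.4.1, on withdrawal from trial treatment, names adverse events as a medical reason and refers the reader to Section 4.1.2.4. Table 3.3.3: 1 sets the entry limits for liver values. In the SAP, Table 6.2: 1 has deviation code C2 for continuing or stopping study medication contrary to the protocol, with any exclusion decided at the medical quality review meeting. SAP Section 7.8.1 plans a table of adverse events leading to treatment discontinuation.

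**The concern.** A permanent stopping rule should give one answer for one set of facts. Here the answer depends on which page is read when the cause of a liver elevation is unequivocally something other than the study drugs. An investigator who goes from Section 3.3.4.1 to Section 4.1.2.4 finds a stopping list that looks complete and has no exception. An investigator who opens the appendix finds the exception twice.

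The first thing at stake is the handling of the individual patient, who could be stopped permanently or continued under the same protocol. The second is the record of what happened. Either action could be coded as a deviation under C2, and the count of discontinuations due to adverse events would depend on the rule the investigator applied.

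**Working it through.** The point is textual. The plan states no figure to reproduce, and no sample size or error rate enters. The check is a comparison of the three statements.

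| Element | Section 4.1.2.4 | Appendix 10.2, opening paragraph | Appendix 10.2, Hepatic item |
|---|---|---|---|
| Drugs | both antibodies | both antibodies | both antibodies |
| Action | permanent discontinuation | permanent discontinuation | permanent discontinuation |
| Transaminases | >5 times ULN | >5 times ULN | >5 times ULN |
| Total bilirubin | >3 times ULN | >3 times ULN | >3 times ULN |
| Exception for another cause | none | yes | yes |

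The Hepatic item reads "transaminase increases >5 times ULN or total bilirubin >3 times ULN (unless unequivocally attributable to another cause", so the exception is not a stray phrase in one paragraph.

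**Step 1: where the texts agree.** If the elevation is drug-related, of uncertain cause or of mixed cause, the exception does not apply and all three statements call for permanent discontinuation.

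**Step 2: where they conflict.** If the elevation is unequivocally due to another cause, Section 4.1.2.4 calls for permanent discontinuation and both appendix statements exempt the patient.

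**Step 3: whether precedence is stated.** It is not. Section 4.1.2.4 describes the appendix only as a source of further information, gives its own rule in full and does not limit that rule to immune-related elevations.

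**Step 4: whether eligible patients can get there.** Table 3.3.3: 1 excludes ALT or AST ">5 X ULN in the presence of liver metastases", so such a patient may enter with values up to the stopping threshold and a non-drug explanation already present. For patients with Gilbert's syndrome the same table excludes total bilirubin only above 3.0 times ULN (or direct bilirubin above 1.5 times ULN), so entry is possible up to the bilirubin threshold. Section 5.2.6.1.4 also foresees non-drug causes of liver injury: the notes to its figure on potential DILI cases name progression and viral hepatitis.

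**Step 5: whether a frequency can be derived.** It cannot. The relative rise needed to reach the transaminase threshold is 5.0 / (entry value) − 1:

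- entry at 4.9 times ULN: 5.0/4.9 − 1 = 2.0%
- entry at 4.0 times ULN: 5.0/4.0 − 1 = 25%
- entry at 3.0 times ULN: 5.0/3.0 − 1 = 67%

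The entry values are illustrative. The documents give no baseline distribution of ALT/AST and no share of patients with liver metastases or Gilbert's syndrome. The figures show that the case can arise, not how often.

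**The case against.** The best defence is that the texts can be read together. Section 4.1.2.4 sends the reader to Appendix 10.2, the appendix is the more detailed text, and the exception stands in two of the three places. An accidental omission from the section is at least as plausible as two competing rules. That may well explain how the difference arose, but it does not remove it. A stopping rule should not rest on the reader inferring that an appendix cited for additional information qualifies a rule stated in full elsewhere.

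A second objection concerns tumour progression in the liver, the obvious example. Under the synopsis, treatment runs only until progression (or unacceptable toxicity or the time limit), and Section 5.1 allows it to continue afterwards only if the investigator, medical monitor and sponsor agree. In many such patients progression would end treatment anyway. This stands, and it narrows the practical scope to elevations without declared progression, agreed treatment beyond progression, and causes other than progression.

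A third concerns the analysis. A reader might infer that the primary result is compromised. The documents do not support that. The endpoint compares uptake in Cycle 1 with uptake up to Cycle 2 Day 8, so a stop after the Cycle 2 scans leaves it unchanged; only a stop before or during that imaging could matter. SAP Section 6.2 defines no per-protocol set, and exclusions under C2 are decided case by case. What remains is possible inconsistency in deviation coding and in the discontinuation table, in a descriptive study of at most 40 patients.

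Finally, SAP Section 4 records that the sponsor terminated the study early. A protocol correction therefore has little left to do for dosing in this trial. The coding question remains for its report, and the wording matters for any reuse of the text.

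**Conclusion.** Wrong as written: an internal inconsistency in the protocol, confined to transaminases above 5 times ULN or total bilirubin above 3 times ULN that are unequivocally attributable to another cause. A reader might infer that any value above the threshold both does and does not require discontinuation. The comparison does not bear that out, because thresholds, drugs and action match in all three places and only the exception differs.

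The conclusion rests on the current text alone and needs no numerical assumption. How many patients it would affect is unknown, and a small required rise such as 2% should not be quoted as the size of the problem, because it follows from the chosen entry value. The consequences that can be shown are two standards for the stopping decision, for deviation code C2 and for the table of adverse events leading to treatment discontinuation.

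**What to change.** Reconcile Section 4.1.2.4 with the opening paragraph and the Hepatic item of Appendix 10.2, so that the liver discontinuation criterion reads identically in all three. Which wording to adopt is a clinical decision for the sponsor and investigators and is not suggested here.

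State also, in the SAP or in the minutes of the report planning meeting, which version governs the coding of deviation C2, and apply it to every liver-related decision to stop or continue.

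The protocol change is one phrase, plus the usual approvals if it is made by amendment. The coding statement is one sentence and needs no new data or analysis.

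### Appendix 10.2 sets a later steroid trigger for Grade 3-4 diarrhea not judged to be colitis (over 1 week) than for Grade 2 diarrhea/colitis (over 3 days)

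*Protocol*

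**What the plan says.** The Diarrhea/Colitis part of Protocol Appendix 10.2 has three consecutive steroid rules:

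- Grade 2: "For Grade 2 diarrhea/colitis that persists greater than 3 days, administer oral corticosteroids".
- Grade 3-4 diarrhea: "For Grade 3 or 4 diarrhea that persists >1 week, treat with i.v. steroids followed by high-dose oral steroids".
- Colitis: "For Grade 3 or 4 colitis, or recurrent colitis of any grade, permanently discontinue BI 754091 and BI 754111, and immediately treat", again with i.v. and then high-dose oral steroids.

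Just before these rules comes the work-up that separates the second from the third: "For Grade 2 or higher diarrhea, consider gastro-intestinal (GI) consultation and endoscopy to confirm or rule out colitis". It is to be considered, and no deadline is given.

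Sections 1.4, 4.1.2.4 and 5.2.6.1.4 refer the reader to this appendix for managing immune-related events. Section 5.2.6.1.4 describes its content as recommendations.

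**The concern.** An investigator who looks up what to do and follows the text starts steroids later in the sicker patient, during the days when colitis is neither confirmed nor excluded. The appendix gives no reason for this order.

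The event is foreseeable. Section 1.4 names diarrhea and, less often, colitis among the main immune-related events, notes rare fatal colitis with this class of drug, and calls steroids the main treatment. It also reports 2 Grade 3 diarrhea cases possibly related to study drugs in the earlier trial of this combination. At stake is the timing of treatment for an individual patient, not any estimate the trial will report.

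**Working it through.** No sample size, error rate or estimate is involved, so the check sets the rules side by side and looks for any other rule that would override them.

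**Step 1: triggers in the Diarrhea/Colitis part of Appendix 10.2**

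| Event | Wait before steroids | Route |
|---|---|---|
| Grade 2 diarrhea/colitis | more than 3 days | oral |
| Grade 3-4 diarrhea | more than 1 week (7 days) | i.v., then high-dose oral |
| Grade 3-4 colitis, or recurrent colitis of any grade | none | i.v., then high-dose oral |

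Difference between the first two triggers: 7 - 3 = 4 days, with the longer wait at the worse grade.

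**Step 2: which courses fall in the gap** (days from first onset at Grade 2 or higher)

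- Grade 3-4 from the start, not judged to be colitis: steroids due after day 7, against day 3 for a Grade 2 event. Gap 4 days.
- Grade 2 at onset, Grade 3 on day 2: the event was never at Grade 2 for more than 3 days, so the Grade 2 rule was not met. Gap again 4 days if the week runs from first onset. The bullet does not say when the week starts; counting from the day Grade 3 is reached would lengthen the gap, not shorten it.
- Grade 2 at onset, Grade 3 on day 5: oral steroids were already due after day 3. Gap in first steroid 0 days.
- Established or clinically judged Grade 3-4 colitis: immediate treatment. No gap.

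**Step 3: is there an earlier trigger elsewhere?** None was found. Section 4.1.2.4 deals with holding and stopping study drugs. Section 4.2.2.1 accepts immunosuppressives for product-related events, Section 4.2.1 leaves other needed medication to the investigator, and the colitis row of Table 10.1: 1 (which includes diarrhea) foresees systemic steroids at any grade. These permit an earlier start; none sets one.

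**Step 4: the rest of the appendix.** Six other instructions give steroids at Grade 3-4:

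- pneumonitis: "For Grade 3-4 events immediately treat with i.v. steroids"
- colitis, as above
- hypophysitis: "For Grade 3 events, treat with an initial dose of" i.v. corticosteroids
- hyperthyroidism: an initial i.v. dose, then oral
- hepatic: i.v. "corticosteroids for 24 to 48 hours"
- renal: "For Grade 3-4 events, treat with systemic corticosteroids"

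None of the 6 states a waiting period. Only 2 of them (pneumonitis and colitis) say that treatment is immediate; the other 6 - 2 = 4 are silent on timing. This is supporting evidence only.

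**The case against.** The strongest reply is that the two bullets do not compare like with like. At Grade 2 the rule covers diarrhea and colitis together and starts an oral drug. At Grade 3-4 the protocol splits by diagnosis, with colitis treated at once and the remaining diarrhea given i.v. and high-dose steroids only if it lasts. A longer wait before a heavier regimen, in patients not thought to have colitis, could be deliberate. This does not explain the order. The Grade 2 rule needs no proof of colitis either, so diagnostic doubt would justify waiting at least as long at Grade 2.

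A second reply is that the 3-day rule carries over to higher grades. The wording is against it. The work-up sentence extends explicitly to grades above 2, the steroid bullet names Grade 2 alone, and Grade 3-4 diarrhea has its own bullet.

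Several points on the other side do stand:

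- Nothing makes endoscopy a condition for the colitis rule. An investigator who judges severe diarrhea to be colitis on clinical signs can treat at once, which narrows the gap.
- Immune-related diarrhea of Grade 2 or higher is an event of special interest (Table 10.1: 1), reportable within 24 hours (Section 5.2.6.2.2). That sets no steroid start, but it brings the sponsor in early.
- The comparison with other organs is soft. Diarrhea is a symptom, its true counterpart is colitis, and four of the six instructions give no timing at all.
- The documents contain no external timing standard. The case rests on the internal inversion.

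**Conclusion.** The point holds as a minor error in safety guidance. For Grade 3-4 diarrhea that is not established or clinically judged to be colitis and did not first meet the Grade 2 trigger, the written steroid trigger is 4 days later than for the milder grade. The 4 days assume that both clocks run from first onset.

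Four stronger readings are tempting, and the documents do not support them:

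- *Earlier steroids are forbidden.* They are not. The appendix is guidance, and Sections 4.2.1 and 4.2.2.1 leave room to start sooner. The fault is in the default.
- *Severe colitis goes untreated for a week.* It does not; the next bullet treats it immediately.
- *The 2 earlier Grade 3 cases show how many patients would be harmed.* They show only that the event occurs. Section 1.4 gives neither their duration nor their treatment. The statement in SAP Section 7.4.1 that nobody was imaged under protocol version 3 concerns PET timing and says nothing about exposure to this appendix. The number affected cannot be estimated.
- *The trial's results are affected.* No planned analysis uses steroid timing.

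Practical weight is further limited because SAP Section 4 records that the sponsor ended the study early.

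**What to change.** Replace the Grade 3-4 diarrhea bullet with text such as:

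*Grade 3 or 4 diarrhea, unless colitis or an immune-related cause has been ruled out: give i.v. steroids and then high-dose oral steroids, no later than when the diarrhea has lasted more than 3 days from first onset at Grade 2 or higher, or at once if it worsens to Grade 3 or 4 after that point. The investigator may start earlier.*

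Leave the Grade 2 and colitis bullets unchanged. Under this rule, diarrhea that is Grade 3 from the start, or worsens on day 2, reaches the i.v. regimen after day 3 at the latest; diarrhea that worsens on day 5 gets it at once. The exception keeps high-dose steroids away from patients in whom colitis or an immune cause has been excluded.

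If any patient is still on treatment, a letter to the centre is not enough. Section 8.1 requires ethics committee and competent authority approval for changes introduced by amendment, and Global Amendment 2, which itself edited this appendix, was to be implemented only after approval. The alternative is an urgent safety measure, if the sponsor judges it to be one. Whether or not anyone is still on treatment, correct the text wherever the sponsor reuses this guidance.

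The cost is one bullet and its approval, with no effect on patient numbers, assessments or analysis. The clinical downside is some additional early steroid use in Grade 3-4 diarrhea that would have resolved or later proves not to be immune-related. The documents give no basis for quantifying it.
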